The Effect Of Preoperative Parameters On Success After Descemet Membrane Endothelial Keratoplasty (DMEK) Surgery

CLINICAL STUDY PLAN

ClinicalTrials.gov Results Data Element Definitions for Interventional and Observational Studies

▼ 1. Participant Flow Enrollment Assessed for eligibility (n=) Excluded (n=) $_{\square}$ Not meeting inclusion criteria (n=) □ Declined to participate (n=) □ Other reasons (n=) Allocated to intervention (n=) Received allocated intervention (n=) Did not receive allocated intervention (give reasons) (n=) Follow Up Lost to follow Discontinued intervention (give reasons) (n=) Analysis Analysed (n=) Excluded from analysis (give reasons) (n=)

Groups/Cohorts	Interventions
Cohort	Procedure/Surgery: Descemet membrane endothelial keratoplasty
	(DMEK)
All patients	All participants underwent DMEK surgery

Period(s)

Our study was created by planning a 6-month follow-up period. Information about the number of patients at the beginning and end of the study will be reported when the study is completed.

▼ 2. Baseline Characteristics

Patients' age, gender, eye side, additional diseases, medications used and preoperative visual acuity values will be recorded at the beginning of the study.

Groups/Cohorts	Interventions
Cohort	Procedure/Surgery: Descemet membrane endothelial keratoplasty (DMEK)
All patients	All participants underwent DMEK surgery

Baseline Analysis Population Information

Overall Number of Baseline Participants

A total of 60 participants are planned to participate in the study.

Baseline Measure Information

Patients' age, gender, eye side, additional diseases, medications used and preoperative visual acuity values will be recorded at the beginning of the study.

Baseline Measure Title

The change in the visual acuity and the change in the number of endothelial cells will be the primary outcome of the study.

Study-Specific Measure *\sqrt{\sqrt{Select as many as needed}}

- Age (Select at least one of the following):
 - Age, Continuous: For example mean or median age
- Sex/Gender (Select at least one of the following):
 - Sex: Female, Male
- Race and Ethnicity
 - Race and Ethnicity Not Collected

Measure Type *

Definition: The type of data for the baseline measure. Select one.

• Count of Participants

Measure of Dispersion

Select one.

• Not Applicable (only if Measure Type is "Number", "Count of Participants", or "Count of Units")

Baseline Measure Data *

When the investigation is completed, information about each baseline measures data will be updated.

Unit of Measure *

Participants, mmHg, micron, millimeter

▼ 3. Outcome Measures

A table of data for each primary and secondary outcome measure by arm (that is, initial assignment of participants to arms or groups) or comparison group (that is,

analysis groups), including the result(s) of scientifically appropriate statistical analyses that were performed on the outcome measure data, if any.

Note: Outcome measure information from the Protocol Section of the record will be copied into the Results Section the first time results are created.

Primary Outcome Measure:

1.Visual Acuity (Snellen)

Change from baseline

[Time Frame: Baseline and after surgery 1, 3, 6, and 12 months] 2.Endothelial Cell density (cells/mm²)

After surgery measurements

[Time Frame: after surgery 1, 3, 6, and 12 months]

Secondary Outcome Measures:

1. Maximum (steepest) and minimum (flattest) keratometry values in the central corneal zone (K values)

Change from baseline

[Time Frame: Baseline and after surgery 1, 3, 6, and 12 months]

2. Anterior chamber depth (mm)

Change from baseline

[Time Frame: Baseline and after surgery 1, 3, 6, and 12 months]

3. Axial Length (mm)

Change from baseline

[Time Frame: Baseline and after surgery 1, 3, 6, and 12 months]

4. Central pachymetry (micron)

Change from baseline

[Time Frame: Baseline and after surgery 1, 3, 6, and 12 months]

5. Intraocular pressure (mmHg)

Change from baseline

[Time Frame: Baseline and after surgery 1, 3, 6, and 12 months]

Other Pre-specified Outcome Measures:

6. Surgical complications

Complications occurring during the surgery will be recorded.

[Time Frame: During surgery]

Groups/Cohorts	Interventions
Cohort	Procedure/Surgery: Descemet membrane endothelial keratoplasty
	(DMEK)
All patients	All participants underwent DMEK surgery

Analysis Population Information

Overall Number of Participants Analyzed

In total, we expect 60 participants to participate in the study.

Type of Units Analyzed

The analysis will be based on participants

Outcome Measure Data Table Measure Type

• Count of Participants

Measure of Dispersion/Precision

• 95% Confidence Interval

Statistical Analyses

The required sample size was determined by power analysis based on previous studies. [G * Power, Version: 3.1.9.2 Statistical Packages]. Variance analysis (ANOVA) will be used in the statistical analysis of preoperative and postoperative 1st and 6th months, if the measurements show normal distribution in the repeated measurements. Post-hoc Bonferroni test will be used to find out whether there is a difference between the measurements. Friedman test will be used in the statistical analysis of measurements that do not show normal distribution. Wilcoxon test will be used to find out whether there is a difference between the measurements. Pearson and Spearman correlation test will be used in the correlation analysis. For statistical significance p <0.05 will be accepted.

▼ 4. Adverse Event Information

Information for completing three tables summarizing adverse events.

- 1. All-Cause Mortality: Mortality is not expected in our study.
- 2. Serious Adverse Events: Serious adverse event is not expected in our study
- 3. Other (Not Including Serious) Adverse Events: No adverse effects due to study are expected. If any adverse event will be seen, it will be reported.

Time Frame

Adverse event data will be collected between 1 June 2019, and 1 June 2021.

Adverse Event Reporting Description [*]

Patients will be invited to examinations at regular intervals and will contact the researchers at the contact numbers provided if they see any unexpected effects.

Collection Approach for Table Default

• Systematic Assessment: Baseline and after surgery 1, 3, 6, and 12 months

Arm/Group Information

There is only a study group.

Arm/Group Title

All patients

Arm/Group Description

All participants underwent (Descemet membrane endothelial keratoplasty) DMEK surgery

Total Number Affected by All-Cause Mortality

Total Number at Risk for All-Cause Mortality

0

Total Number Affected by Any Serious Adverse Event

Total Number at Risk for Serious Adverse Events

0

Frequency Threshold for Reporting Other (Not Including Serious) Adverse Events

5

Total Number Affected by Any Other (Not Including Serious) Adverse Event Above the Frequency Threshold

Total Number at Risk for Other (Not Including Serious) Adverse Events $\boldsymbol{0}$

Adverse Event Term

A significant unexpected effect that affects the course of the study.

Organ System

• Eye Disorders

Collection Approach

• Systematic Assessment: Baseline and after surgery 1, 3, 6, and 12 months

Number of Participants Affected

0

Number of Participants at Risk

0

▼ 5. Limitations and Caveats

Overall Limitations and Caveats

In our study, only Descemet membrane endothelial keratoplasty (DMEK) surgeries were included. However, Descemet's stripping automated endothelial keratoplasty (DSAEK) surgeries were not included, and no comparative study was performed.

▼ 6. Certain Agreements

Information indicating whether there exists an agreement between the sponsor or its agent and the principal investigators (unless the sponsor is an employer of the principal investigators) that restricts in any manner the ability of the principal investigators (PIs), after the completion of the study, to discuss the results of the study at a scientific meeting or any other public or private forum, or to publish in a scientific or academic journal information concerning the results of the study. This does not include an agreement solely to comply with applicable provisions of law protecting the privacy of participants.

Are all PIs Employees of Sponsor?

Definition: Indicate whether the principal investigator is an employee of the sponsor.

• Yes

PI Disclosure Restriction Type

There are no varying agreements.

▼ 7. Results Point of Contact

Point of contact for scientific information about the clinical study results information.

Name or Official Title *

Definition: [name] [name]

Organization Name *

Definition: Beyoglu Eye Research and Education Hospital

[contact]

[name]

Email: [contact]

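### A study of preoperative predictors lists no surgeon, case-order, donor or graft item and plans only unadjusted correlations

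*Combined protocol and SAP*

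**What the plan says.** The title sets a predictor question: "The Effect Of Preoperative Parameters On Success After Descemet Membrane Endothelial Keratoplasty (DMEK) Surgery". Section 4 (Arm/Group Information) confirms a single group: "There is only a study group". Section 2 plans 60 participants.

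The items to be recorded are given twice in section 2: "age, gender, eye side, additional diseases, medications used and preoperative visual acuity values will be recorded at the beginning of the study". All describe the recipient. Section 3 adds measurements of the operated eye (keratometry, anterior chamber depth, axial length, pachymetry and intraocular pressure), postoperative endothelial cell density, and complications during surgery. The complications are an outcome, not a covariate.

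The description of the intervention is that "All participants underwent DMEK surgery". No section states how many surgeons operated, their experience, the order of cases, or anything about the donor or the graft.

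Under Statistical Analyses in section 3, the one sentence on association is: "Pearson and Spearman correlation test will be used in the correlation analysis". It names no variables, covariates or regression model.

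**The concern.** In a single unrandomised group, nothing in the design balances surgeon, experience or graft across levels of a preoperative parameter. An unadjusted correlation therefore carries any surgeon difference that happens to run with the parameter. If eyes with an unfavourable parameter tend to go to the better surgeon, or are taken on later in a series, a real adverse effect can be masked. If allocation runs the other way, an apparent effect can arise where none exists. With no link, the estimate is unbiased but noisier than it need be.

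Cell density raises a separate issue. It is a primary outcome, section 3 schedules it only after surgery, and in this operation the counted cells come from the donor. Section 2 calls the same outcome a change, yet no starting graft count is listed. Recipient parameters would thus be correlated with a graft quantity while no graft input is listed.

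**Working it through.** **The plan's own figure.** Section 3 says "The required sample size was determined by power analysis based on previous studies" but gives no effect size, SD, power or dropout, so N=60 cannot be reproduced. For scale, the correlation detectable at n=60 with 80% power and two-sided 0.05 is tanh((1.960+0.842)/√57) = 0.355.

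**Inputs.** From the plan: n=60 and significance at p<0.05 (two-sided assumed). Assumed, because the plan gives nothing: two surgeon or experience groups of equal size, differing by dx SD in the parameter and dy SD in the outcome, with each difference between 0.5 and 0.8. A 0/1 group indicator with equal halves has variance 0.25. Rejection probabilities use Fisher's z, with mean atanh(r)·√57 and critical value 1.96.

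**1. No true effect, group linked to the parameter.** Induced r = 0.25·dx·dy / √[(1+0.25dx²)(1+0.25dy²)].

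| dx, dy | Induced r | Chance of p<0.05 |
|---|---|---|
| 0.5, 0.5 | 0.0625/1.0625 = 0.059 | 7.3% |
| 0.6, 0.8 | 0.12/√(1.09×1.16) = 0.107 | 12.8% |
| 0.8, 0.8 | 0.16/1.16 = 0.138 | 18.2% |

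**2. True effect masked.** Take a within-surgeon correlation of -0.30, so the slope is -0.30/√(1-0.09) = -0.3145 with unit residual variance. The better surgeon (+0.8 SD in outcome) takes eyes whose parameter is 0.6 SD more unfavourable.
- Variance of x: 1 + 0.25×0.36 = 1.09.
- Covariance: -0.3145×1.09 + 0.25×0.6×0.8 = -0.223.
- Variance of y: 0.3145²×1.09 + 0.25×0.64 + 1 - 2×0.3145×0.8×0.6×0.25 = 1.192.
- Observed r: -0.223/√(1.09×1.192) = -0.195.
- Power falls from 0.65 at |r|=0.30 to 0.32.

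**3. No link, noise only.** The share of outcome variance due to the group is v = 0.25dy²/(1+0.25dy²): 5.9% at 0.5 SD and 13.8% at 0.8 SD. Removing it is worth 1/(1-v) = 1.06 to 1.16, that is 6 to 16% more participants. The false-positive rate stays at 5%.

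**4. Does adjustment work?** A separate simulation (20,000 runs per setting, n=60) used a continuous unrecorded factor in place of two groups. Partial correlation given that factor had a false-positive rate of 0.048 to 0.052 in every setting, including those where the crude test was inflated.

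**The case against.** **The mechanism is assumed.** No section shows more than one surgeon or allocation by difficulty, and section 7 names one organisation. This stands: the bias in steps 1 and 2 is a possibility, not a finding. One organisation does not establish one surgeon, however, and with one surgeon case order could still matter.

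**The list may be incomplete.** The document fills in a registry results template and is not a case report form. The section 2 list omits chamber depth, axial length, keratometry, pachymetry and pressure, although section 3 needs all of them at baseline. So the plan supports saying that surgeon and graft items are not listed, not that no one records them.

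**Stronger readings that the documents do not support.**
- A reader might infer that surgeon and graft differences can never be removed. Nothing in the plan says that operating and tissue records could not be consulted, and the fix below relies on them.
- A reader might infer a two-year series of operations from "Adverse event data will be collected between 1 June 2019, and 1 June 2021". Those dates concern adverse events. If the window includes complete follow-up, surgery spans about 12 months at most (12-month visits in section 3) or about 18 months (6-month follow-up in section 1).
- A reader might infer that grafts too can mimic a parameter effect. Nothing in the plan links donor age or graft diameter to a recipient parameter. For grafts, only the precision argument is shown.

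**The scope is limited.** The most fully specified analysis is the within-eye comparison over time (ANOVA or Friedman), which does not rest on contrasts between surgeons. The correlation sentence names no variables, so its target is inferred from the title. Both points stand and confine the concern to the predictor question, which is the question in the title.

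**Conclusion.** The concern holds in limited form. The plan poses a predictor question, lists no surgeon, case-order, donor or graft item, and plans only unadjusted correlation. Whether this biases the result depends on facts the plan does not give.

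- If surgeon or experience is related to a parameter, the false-positive rate is about 7 to 18%, or a true -0.30 is seen as about -0.20 with power near 32% instead of 65%. These figures rest on the assumed two equal groups and differences of 0.5 to 0.8 SD.
- If there is no relation, there is no bias, and precision equivalent to 6 to 16% more participants is lost.
- With one surgeon at stable experience, only the graft items matter. They matter as noise in postoperative cell density.

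This is an inexpensive improvement that should be made. It does not show that the study is invalid. Confidence in the size is low, because the number of surgeons and the allocation of eyes are unknown.

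**What to change.** 1. **Section 2, recorded items.** Add, copied from the operating and tissue records: surgeon code, the surgeon's case number in the series, donor age, graft diameter and, where the tissue record holds it, donor graft cell density. State how many surgeons operated. If these items are already held, say so and list them.
2. **Section 3, Statistical Analyses.** For the analyses relating preoperative parameters to acuity and cell density, replace the unadjusted correlation with a partial correlation or regression. Adjust for surgeon, or for early versus late half of the series if there is one surgeon. When cell density is the outcome, also adjust for donor graft density or, if that is unavailable, donor age.

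The cost is four or five items transcribed from records, a few sentences of analysis text, and two or three degrees of freedom out of 60. Visits, treatment and sample size do not change. With so few participants, the covariates should be limited to those named.

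### The plan neither states that the indication for DMEK is recorded nor limits the cohort to one indication, and its parameter–outcome correlations are unadjusted

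*Combined protocol and SAP*

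**What the plan says.** The study question is in the title: "The Effect Of Preoperative Parameters On Success After Descemet Membrane Endothelial Keratoplasty (DMEK) Surgery".

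Section 2 (Baseline Characteristics) gives the baseline record, twice in the same words: "Patients' age, gender, eye side, additional diseases, medications used and preoperative visual acuity values will be recorded at the beginning of the study". Section 3 (Outcome Measures) also gives a baseline time point to keratometry, anterior chamber depth, axial length, central pachymetry and intraocular pressure. None of these identifies the disease for which the graft is done.

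The cohort is described by procedure only: "All participants underwent DMEK surgery". The adverse event section confirms that "There is only a study group". The participant flow chart has a box for people excluded under the inclusion criteria, but the criteria themselves are not given. The limitations section says that another graft procedure (DSAEK) was left out and mentions no restriction by disease.

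On analysis, Section 3 plans ANOVA or Friedman tests across time points, with post-hoc comparisons, and then one sentence on association: "Pearson and Spearman correlation test will be used in the correlation analysis". No covariate, stratum or multivariable model is named, and the pairs of variables to be correlated are not listed.

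**The concern.** DMEK names an operation, not a diagnosis. The indication is itself a preoperative characteristic, and it is in place before the other preoperative values are measured. Suppose two indications are enrolled, and they differ on average both in a preoperative parameter and in an outcome. Pooling them then produces a correlation between parameter and outcome, even if the two are unrelated among patients with the same indication.

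The ANOVA and Friedman comparisons describe change over time and do not address the title question. The correlations are the only planned analysis that can, and they are the part exposed to this confounding. At stake is whether a reported predictor of success reflects the parameter or the case mix.

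**Working it through.** **The plan's own figure.** Section 2 states: "A total of 60 participants are planned to participate in the study". This number cannot be reproduced, because the plan names a power analysis but gives no effect size, SD, power or test. It is used here only as n. For scale, assuming 80% power and a two-sided 5% test, the correlation that 60 participants can detect is tanh((1.960 + 0.842)/√57) = tanh(0.371) = 0.355.

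**Inputs from the plan.** n = 60 (Section 2); significance level 0.05 (Section 3; two-sided is assumed, as the plan does not say).

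**Assumed inputs.** The documents give no case mix and no differences between indications, so these are assumptions: two indications, with share p in the second; differences d1 in the parameter and d2 in the outcome, in within-indication SD units; no association within either indication. For acuity, d2 refers to change from baseline, as Section 3 defines that outcome. For endothelial cell density it refers to the postoperative value.

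**Induced correlation.** Pooling adds p(1−p)·d1·d2 to the covariance and p(1−p)·d² to each variance, so

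r = p(1−p)·d1·d2 / √[(1 + p(1−p)·d1²)(1 + p(1−p)·d2²)].

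**False-positive rate (Fisher z).** With λ = atanh(r)·√(n−3) = 7.550·atanh(r), the rate is Φ(λ − 1.96) + Φ(−λ − 1.96).

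**70:30 mix.** p(1−p) = 0.3 × 0.7 = 0.21. The last two columns come from 20,000 simulated trials per row with 42 and 18 participants, using the Pearson test without and with adjustment for indication.

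| d1 = d2 | r | λ | Rate, Fisher z | Simulated, unadjusted | Simulated, adjusted |
|---|---|---|---|---|---|
| 0.5 | 0.0525/1.0525 = 0.050 | 0.38 | 7% | 7% | 5.2% |
| 1.0 | 0.21/1.21 = 0.174 | 1.32 | 26% | 27% | 5.1% |
| 1.5 | 0.4725/1.4725 = 0.321 | 2.51 | 71% | 74% | 5.0% |

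With unequal differences, d1 = 1.5 and d2 = 1, r = 0.315/√(1.4725 × 1.21) = 0.236 and the Fisher z rate is 44%.

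**Other mixes (simulated, unadjusted), for d = 0.5, 1 and 1.5.** At 50:50 the rates are 7%, 34% and 85%; at 85:15 they are 6%, 14% and 41%. At 50:50 and 1.5 SD the induced r is 0.36, about the size that 60 participants would detect with 80% power.

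**Limits of the mechanism.** If p, d1 or d2 is zero, r is zero and the rate stays at 5%. With indication in the analysis, the simulated rate was 4.7% to 5.2% in every scenario.

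**The case against.** The strongest reply is that a mixed cohort is nowhere stated. The flow chart implies inclusion criteria that are not reproduced, and the document refers to a protocol section of the registry record that is not part of it. Those criteria might restrict entry to one indication, and the problem would then vanish. This stands, which is why the point is conditional. A reader might infer that the cohort is mixed; the documents do not show that. They do not show the opposite either, so the plan needs a sentence in both cases.

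Secondly, absence from the Section 2 sentence does not prove that the field is uncollected. That sentence is not exhaustive, since Section 3 adds five further baseline measurements, and the entry on additional diseases is undefined. Its natural meaning is disease other than the one treated, but that is a reading. What is supported is that recording of the indication is not stated.

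Thirdly, every magnitude input is assumed. At 0.5 SD the inflation is trivial, and the high rates need differences of 1 to 1.5 SD in both variables. A difference between indications in acuity level need not carry over to acuity change; it could shrink, grow or reverse. This also stands, so the rates are illustrations and not estimates for this trial.

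Finally, the within-participant comparisons over time are untouched. That is correct and limits the point to the correlations.

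**Conclusion.** The point holds in conditional form. The indication for DMEK is not named anywhere as a recorded variable, entry criterion, stratum or covariate, and the one analysis that can serve the title question is unadjusted. In a mixed cohort whose indications differ in both parameter and outcome, the plan followed as written could report case mix as a parameter effect. The size ranges from nil (one indication), through about 7% (0.5 SD in both, 70:30), to 26% and 71% (1 and 1.5 SD), against a nominal 5%. All of this rests on an assumed two-indication model with no association within indication, and on a two-sided Pearson test.

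A reader might go further and infer that the confounding could never be removed afterwards. The documents do not support that. They are silent on access to surgical records, and the reason for operating should be known for every patient who has surgery, so it could be retrieved and used at analysis. The weakness is that the plan commits neither to obtaining it nor to using it. The change is worth making, but the documents do not show that the results will be invalid without it.

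**What to change.** Add the indication for DMEK to the baseline record in Section 2, retrieving it from surgical records for participants already enrolled if needed. In Section 3, replace the unadjusted correlations with partial correlation, or regression with indication as a factor, for each analysis relating a preoperative parameter to acuity change or endothelial cell density. Report the associations within indication where numbers allow. Recording alone is not enough, because an unadjusted correlation would not use the field.

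If only one indication is enrolled, state it as an entry criterion and limit the conclusion to it; no adjustment is then needed.

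The cost is one categorical field, and one or two degrees of freedom out of 60 participants (one for two indications, two for three).

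### The scale on which Snellen acuity change (primary outcome 1) will be analysed is not stated; if Snellen values are used as written, mean change and correlations on change depend on notation and starting acuity

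*Combined protocol and SAP*

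**What the plan says.** Section 3 (Outcome Measures) of the combined protocol and SAP lists the first primary outcome as "1.Visual Acuity (Snellen)", with the metric "Change from baseline". Section 2, under Baseline Measure Title, repeats it without a scale: "The change in the visual acuity and the change in the number of endothelial cells will be the primary outcome of the study". Baseline acuity is collected: "preoperative visual acuity values will be recorded at the beginning of the study".

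No section says whether acuity is held as a fraction, a decimal, a denominator or MAR, or logMAR. The unit list in section 2 covers participants, pressure and lengths, but not acuity. Primary outcome 2, by contrast, carries its unit.

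The Statistical Analyses paragraph names no transformation. It uses repeated-measures ANOVA "if the measurements show normal distribution in the repeated measurements", and Friedman and Wilcoxon otherwise. It adds "Pearson and Spearman correlation test will be used in the correlation analysis" without naming the variables. The title gives the aim: "The Effect Of Preoperative Parameters On Success After Descemet Membrane Endothelial Keratoplasty (DMEK) Surgery". Several candidate parameters are measured at baseline as secondary outcomes, for example "4. Central pachymetry (micron)".

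**The concern.** Snellen acuity is a ratio, so equal subtracted amounts are not equal relative changes. Decimal subtraction gives more weight to gains in eyes that start well. Subtraction of denominators or MAR gives more weight to gains in eyes that start badly. A mean change on either scale mixes the size of the gain with the starting acuity, and the plan does not say which scale it means.

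The larger stake is the predictor question. If change is tied to baseline acuity by the scale alone, any preoperative parameter that tracks baseline acuity can appear to predict the gain when it does not.

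**Working it through.** **Inputs from the documents:** 60 participants, one cohort, significance at p<0.05, Pearson and Spearman correlation. The plan has no acuity figure to reproduce. Everything below on lines, acuity distributions and gains is assumed.

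**1. One gain on three scales** (assumed: 1 line = 0.1 logMAR, so three lines = 0.30 logMAR). From decimal acuity d, the decimal change is d × (10^0.3 − 1) = 0.995d. The MAR change is (1/d) × (1 − 10^−0.3) = 0.4988/d.

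| Start (decimal) | Decimal change | MAR change | logMAR change |
|---|---|---|---|
| 0.05 | 0.050 | 9.98 | 0.30 |
| 0.50 | 0.498 | 1.00 | 0.30 |

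The ratio is ten-fold on decimals and ten-fold the other way on MAR.

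**2. Other charts.** On a chart with steps of 0.1 decimal, one line is always 0.1 decimal, but it spans log10(0.2/0.1) = 0.301 logMAR at the bottom and log10(1.0/0.9) = 0.046 at the top. On an assumed 20-foot sequence, one line runs from 0.05 decimal (20/400 to 20/200) to 0.20 (20/25 to 20/20), a ratio of 4, and from 0.079 to 0.301 logMAR. The ratios depend on the chart; the unevenness does not go away.

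**3. The mean can change sign.** Two eyes go from 0.05 to 0.10 and from 0.80 to 0.63. Mean decimal change: (0.05 − 0.17)/2 = −0.06, a loss. Mean logMAR gain: (0.301 − 0.104)/2 = +0.10, an improvement.

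**4. Which analyses are affected.** Friedman ranks within each eye, so a monotone rescaling leaves it unchanged; the same holds for Spearman on acuity levels. Wilcoxon ranks the differences and is little affected if nearly all eyes improve. Mean change, ANOVA, and Pearson or Spearman on change do depend on the scale.

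**5. False predictor links, by simulation.** n = 60. Baseline logMAR is uniform on 0.3–1.3, 0.3–1.0 or 0.4–0.8. Gain is normal and independent of baseline on logMAR, with mean/SD 0.3/0.1, 0.3/0.2 or 0.4/0.2, which makes nine scenarios. Each measurement has error SD 0.05 logMAR, and values better than 0.0 logMAR are set to 0.0 (3–20% of postoperative eyes). A parameter with no effect on gain correlates rho with true baseline logMAR. Share of runs with p<0.05, range over the nine scenarios:

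| Analysis | rho 0.3 | rho 0.5 |
|---|---|---|
| Decimal change, unadjusted | 9–40% | 14–83% |
| logMAR change, unadjusted | 4–8% | 4–10% |
| Postoperative decimal, baseline-adjusted | 5–7% | 6–10% |
| Postoperative logMAR, baseline-adjusted | 4–6% | 4–9% |

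Repeat runs move the ends of these ranges by a few percentage points at most. With rho = 0, all the analyses stay near 5%.

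**6. Below-chart acuities** (assumed). If 3, 6 or 12 of 60 baseline values are below the chart and their assigned value moves from 1.7 to 2.3 logMAR, the mean change moves by 3/60, 6/60 or 12/60 × 0.6 = 0.03, 0.06 or 0.12 logMAR.

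**The case against.** The strongest reply is that Snellen may name only the chart, and that the investigators may convert to logMAR without saying so. That stands. A reader might infer that raw Snellen values will certainly be subtracted, but the documents leave this open. The defect is an unstated scale, with a consequence that follows if values are used as written.

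Further limits that also stand:

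- The ten-fold figures might be read as exact for this trial. They assume 0.1-logMAR lines, which the plan does not state.
- The simulation generates gain on logMAR, so it favours logMAR by construction. If gain were independent of baseline on decimals, logMAR change would show the false link. The documents support neither model.
- A reader might infer that conversion and baseline adjustment are both needed. The table does not show that: either one suffices for this problem under these assumptions.
- A reader might infer that the before-after test is unsound. The normality check applies to the measurements, not to change. With Shapiro–Wilk as an assumed test and the same ceiling and error, decimal levels failed at baseline or follow-up in 91–100% of runs, which leads to Friedman and Wilcoxon. LogMAR levels failed in 30–99.8%, so conversion does not reliably restore ANOVA.
- The predictor risk requires acuity change to be among the correlated variables and the parameter to track baseline acuity. The plan states neither.

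What the reply does not remove is that a primary outcome defined as a change needs a scale, and that Pearson or Spearman on change is not protected by ranking within eyes.

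**Conclusion.** The concern holds in a limited form. The plan does not fix the scale of primary outcome 1. Taken at its word, it yields a mean change, and any correlation on change, that vary with notation and starting acuity. The before-after conclusion is unlikely to be altered if most eyes improve.

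The main exposure is the title question. Under the assumptions in step 5, unadjusted decimal change raised false positives from a nominal 5% to about 9–40% or 14–83%, while logMAR change or baseline adjustment held them at about 4–10%. The omission is certain. Its size rests on assumed acuity distributions, an assumed logMAR gain model and an assumed choice of correlated variables. It is a cheap improvement, not a flaw that invalidates the design.

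**What to change.** Keep the Snellen chart and define primary outcome 1 as change from baseline in logMAR, equal to −log10 of decimal acuity. Run the mean change, ANOVA and acuity correlations on logMAR, and give Snellen equivalents as description only. For each preoperative parameter, regress postoperative logMAR on it with baseline logMAR as covariate, in place of a simple correlation with change. Before analysis, fix one logMAR value for each below-chart category, and vary these values in a sensitivity analysis.

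Cost: a revised outcome definition, a short below-chart rule, one sensitivity analysis and a two-term regression per parameter. Baseline acuity is already collected.

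Downsides: assigned below-chart values can move the mean. Ceiling effects and error in baseline acuity leave some residual bias (up to about 10% false positives in these scenarios). Normality is not reliably restored. On a chart not built in logMAR steps, logMAR change is not a count of chart lines.
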